A clinic nurse will be put on the delegation log to cover [name] during any absence. For that reason the early contact letter and permission to contact letter will be maintained on this ethics approval. Whenever the clinic nurse covers for [name] early contact role, the early contact letter and permission to contact letter will be used to adhere with section 55 (section 34) of the Health Information Act. This role will be documented on the delegation log. Potential participants will be identified by clinic nurses/physician who will be made aware of the inclusion criteria. Clinic nurses will ask potential participants if they would be willing to be approached by a study investigator. If so, a clinic nurse will contact a member of the study team. Recruitment will be achieved by approaching eligible patients in the clinic by a member of the study team that is not the most responsible physician (research coordinator) to prevent undue pressure.

Given that 10 healthy adult participants will be recruited from the study team for stage 1, we will take additional steps to prevent undue pressure. The study team will be made aware eligibility. Interested persons have been asked to contact the study coordinator. The study coordinator will complete the consenting process. The study PI/team will be available for further discussion. It will be clearly stated that participation is completely voluntary and that the participant may withdraw consent at any point without it impacting their role/credit in this study, their employment or future medical care.

Study will be performed in two stages.

Stage 1 (pre study): To calibrate Medbike with reference standard cardiopulmonary exercise test (CPET), and to determine patient tolerance to maintenance of exercise intensity to varying workload in children with Fontan for planning of optimal exercise regimen.

Stage 1A: The program has two retrospective calibration samples already that will be used. Consent will not be obtained given that the data is anonymized and medical records/other identifying information will not be obtained. We will also recruit 10 healthy adult participants prospectively to calibrate the MedBike. VO₂ and CPET will be set at a constant workload between 25W and 125W. Exercise will be repeated after 2 hours of rest on the Medbike with the same setting and VO₂ measures. This visit will take 3 hours to complete.

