Stage 1B: We will recruit 10 patients with Fontan physiology to undergo a baseline standard CPET. Consistent with standard guidelines (ATS/ACCP statement on cardiopulmonary exercise testing, Am J Respir Crit Care med 2003; 167:211-277), exercise workload will be increased progressively such that peak oxygen consumption is achieved in 8-12 minutes. Oxygen consumption, CO₂ production, ventilation, arterial saturation (SpO₂) and blood pressure will be monitored throughout each exercise test.

Stage 1B will be completed in two visits.

- Visit 1: Participants will perform a standard CPET and VO₂ will be measured. This visit will take 1 hour to complete. From the results of this baseline CPET, a high-intensity interval training (HIIT) program will be designed for the subjects (described below).
- Visit 2: Participants will perform the designed HIIT program using the MedBike. This will consist of a 5-minute warm up at 30% of the subject's peak power output (based on results of the baseline CPET study). There will then be 7 bouts of high-intensity interval bursts. Each burst will consist of 2-minutes at 70-90% of peak power output and a 1-minute rest at 40-50% of peak power output. The subjects will then end with a 5-minute cool down at 30% peak power output. An exercise physiologist will be present and will make changes to the interval bursts based on the subject's perceived difficulty and workload. The program is 30-minutes in total. We anticipate

CONFIDENTIAL

This material is the property of individual. No part of it may be transmitted, reproduced, published, or used by other persons without written authorization.

that Visit 2 will take approximately 1-hour to complete with set-up, orientation, and sizing of the MedBike to the subject. In the room with the subject will be an exercise physiologist/technician capable of troubleshooting issues with the MedBike and associated devices for data collection. There will also always be a supervising physician with training in Pediatric Advanced Life Support (PALS), who will continuously monitor the subject's vital signs and the subject's overall clinical status. A 5-10 minute questionnaire will be administered. The purpose of this short questionnaire is to learn a bit more about the participants experience using our video-game tele-medicine exercise bike, the MedBike.

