Any adverse events such as profound desaturation (oxygen saturations fall of $> 10\%$ points for greater than 1 min, chest pain and ECG changes consistent with ischemia (ST depression or elevation in 2 consecutive leads), reducing blood pressure during exercise $> 20\text{mmHg}$, development of tachyarrhythmia (atrial or ventricular) and any bike injury, will result in immediate stoppage of exercise regimen and evaluation by the onsite medical personal, if necessary pediatric cardiology consultation.

The impact of the exercise program on patient and parental perceptions of the patient's physical capacity will be evaluated using qualitative methods, as well as health related quality of life questionnaires. Patient and parents will be interviewed prior to, and at the end of, the exercise training as to their perceptions of the influence of physical activity in the presence of complex CHD.

Primary outcome: Exercise capacity assessed as the change in max VO_2 pre- vs. post- completion of the HIIT exercise program. Hypothesis- we will observe an increased in VO_2 max of 15%.

CONFIDENTIAL

This material is the property of individual. No part of it may be transmitted, reproduced, published, or used by other persons without written authorization.

Secondary outcomes: a) Patient and parental perception of a CHD patient's safety and limitations while performing physical activity through a successful physical rehabilitation program; b) adverse events (safety profile of exercise program).

Inclusion Criteria:

Stage 1A – Retrospective calibration records, prospectively recruited healthy adults 18+

Stage 1B: SV patients with Fontan circulation age 10 - 18 years.

Stage 2 - SV patients with Fontan circulation age 10 - 18

Exclusion Criteria: Patients with cardiac arrhythmias, persistent low resting oxygen saturation of $< 85\%$, severe ventricular dysfunction on the most recent clinical echocardiogram, patients with reports of chest pain on exertion, and those in whom their cardiologist has restricted their exercise for any reason.

Statistical Plan

Sample Size

Stage 1A:

Two retrospective samples will be included. Ten healthy adults will be recruited prospectively.

Stage 1B:

10 patients with Fontan physiology.

Stage 2:

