To detect a clinically relevant change of 15% in max VO_2 with power of 0.8, alpha of 0.05 and effect size of 1.08 with the an anticipated mean peak VO_2 28.2 ml/kg/min \pm 6.1, the calculated sample size is 9. We will recruit 15 Fontan patients in anticipation of up to 30% failure to complete study exercise regimen.

Statistical Methods:

All data will be reported as median with ranges. Comparison between pre and post exercise training data will be tested using paired Wilcoxon signed rank sum. Significance is present when $p < 0.05$.

The Research Team:

This research will be lead by [name], who is a proven investigator with 25 peer- reviewed publications in the last 5 years. The co-investigators include [name], a heart failure specialist and [name], the team lead of the Division's Single Ventricle Outcomes Team that is supported by a WCHRI- funded fulltime research coordinator. This team is also supported by the Department of Pediatrics and AHS, with 3 funded Clinical Research Fellows attached to the Division. Our collaborators [name], [name] and [name] are recognized experts in their respective fields of computing science, exercise physiology and qualitative research of family outcomes related to SV, all with extensive success in their research endeavor.

Anticipated Outcomes and Impact:

CONFIDENTIAL

This material is the property of individual. No part of it may be transmitted, reproduced, published, or used by other persons without written authorization.

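### Stage 1A calibration has no stated agreement analysis: medians with ranges per device ignore the pairing and can hide errors that cancel

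*Combined protocol and SAP*

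**What the plan says.** Under Study Procedures, Stage 1 (pre study) has the aim of calibrating the MedBike against CPET as the reference standard. For Stage 1A: "We will also recruit 10 healthy adult participants prospectively to calibrate the MedBike". The load "will be set at a constant workload between 25W and 125W", and then "Exercise will be repeated after 2 hours of rest on the Medbike with the same setting and VO₂ measures". The design is therefore paired: same adult, same setting, both devices.

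Under Statistical Plan, Sample Size, Stage 1A has counts only: "Two retrospective samples will be included. Ten healthy adults will be recruited prospectively". Statistical Methods then gives one reporting rule for everything, "All data will be reported as median with ranges", and one test, a paired Wilcoxon signed-rank test, whose stated scope is pre- versus post-training data. No section mentions a within-person difference between devices, a bias estimate, limits of agreement, an acceptable limit, or how the retrospective samples enter.

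**The concern.** Calibration asks how far the MedBike departs from the reference for the same person at the same load, and whether that departure changes with load. A median and range for each device answers neither part. It treats the two sets of tests as unrelated, and if adults are tested at different loads the range mostly reflects the loads chosen.

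The answer matters for the later stages. In Stage 1B the baseline CPET fixes each child's peak power, and the MedBike session is set as percentages of it: "Each burst will consist of 2-minutes at 70-90% of peak power output and a 1-minute rest at 40-50% of peak power output". Stage 2 applies the same programme. A load discrepancy between the devices would alter the intensity actually delivered, and so which programme the safety and efficacy results describe.

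**Working it through.** The plan has no calculated figure for Stage 1A to reproduce. Its only calculated sample size, 9, belongs to Stage 2 and does not bear on this point.

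**Inputs from the documents:** 10 adults, loads of 25-125 W, same setting on both devices, median with range.

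**Assumptions, not in the documents:** 10 evenly spaced loads; VO₂ rising linearly with load from 500 mL/min at 0 W, by 10.8 mL/min per W in step 1 and 10 in steps 2 and 3; between-person SD of the intercept 15% and per-test CV 3-8% in steps 2 and 3.

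**1. A noise-free example of errors that cancel.** VO₂ = 500 + 10.8 × W.
- Reference: median 1310, range 770-1850 mL/min.
- MedBike with load errors, in order of load, of 0, +20, −20, +20, −10, +10, −20, +20, −20, 0 W: median 1310, range 770-1850, identical to the reference.
- SD of the errors = √[(6 × 400 + 2 × 100)/9] = √288.9 = 17.0 W. Limits of agreement = ±1.96 × 17.0 × 10.8 ≈ ±360 mL/min.
- The largest relative error is 20/36.1 = 55% of the set load.

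The paired differences show at once what the two summaries do not.

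**2. An error in one direction (gain).** The middle load is 75 W, so the expected shift in the median is 75 × 10 × the gain error: 94 mL/min for 12.5%, 150 for 20%, 225 for 30%. With an accurate bike, the difference in medians has a simulated SD of about 36 mL/min at CV 3% and 56 at CV 5%. Its central 90% range is therefore about ±1.645 × 36 = ±59 and ±1.645 × 56 = ±92. The chance that a real error falls inside that range is about:
- 12.5%, CV 3%: Φ((59 − 94)/36) = 0.17
- 12.5%, CV 5%: Φ((92 − 94)/56) = 0.49
- 20%, CV 5%: Φ((92 − 150)/56) = 0.15

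Large errors in one direction are usually visible. A 12.5% error at CV 5% is a coin toss, and the plan provides no interval by which to judge it.

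**3. An error that changes sign.** Let the load error be 20% of the distance from 75 W. In simulation the two medians differ by about 0 on average. The MedBike range is wider by about 190 mL/min, but the SD of that difference is about 78 at CV 3% and 120 at CV 5%, so it is a noisy signal. Regressing the paired differences on workload (joint test of intercept and slope) detects this error in roughly 76%, 39% and 17% of trials at CV 3%, 5% and 8%. A signed-rank test on the same differences detects it in 1-4%.

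**4. What 10 paired tests can estimate.** With t = 2.262 on 9 df and SD the standard deviation of the paired differences:
- Bias, 95% CI half-width: 2.262/√10 = 0.72 SD.
- Each limit of agreement, 95% CI half-width: 2.262 × √(1/10 + 1.96²/18) = 1.27 SD.

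At CV 5% the SD of the ratio is 5% × √2 = 7.07%. The bias is then known to ±5.1%, and the limits of agreement lie at about ±13.9%, each with its own uncertainty of ±9.0%.

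**The case against.** Several counter-arguments have force.

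- **The stated summary is not blind.** A reader might infer that medians with ranges look the same for an accurate and a badly miscalibrated bike. The documents and the arithmetic do not support that: offsets and gain errors move the median, and sign-changing errors tend to alter the range. Nor does it help to note that the MedBike median would lie inside the reference range. That range spans about 1,000 mL/min by design, so almost any error passes.
- **The signed-rank test is not useless here.** For a 12.5% gain error it rejects in about 99%, 76% and 38% of trials at CV 3%, 5% and 8%. But the plan does not apply it to Stage 1A, it misses errors that change sign, and non-significance in 10 adults is not agreement.
- **All data could include within-person differences.** Their median and range would be informative: in the first example, 0 (−216 to 216) mL/min. The plan does not say that differences are computed.
- **The consequence is softened.** An exercise physiologist may change the intervals, and heart rate, blood pressure, saturation and perceived exertion are monitored at each session. The primary outcome is change in max VO₂ by CPET, so MedBike load error does not enter its measurement. Stage 1A is labelled pre-study and is neither a primary nor a secondary outcome. This stands and lowers the severity. Adjustment by perceived difficulty does not, however, show what load was delivered.
- **Prototype testing was already done.** Anticipated Outcomes and Impact says so but gives no results, and the sponsor still plans Stage 1A.

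**Conclusion.** The point holds as a minor one. Stage 1A has a calibration aim and a paired design, but the only rule covering it produces summaries per device that discard the pairing and workload and give no bias estimate or interval. Large errors in one direction would show; errors that cancel across people or workloads can be missed, and moderate ones cannot be told from noise. The percentages rest on the assumed VO₂-load line, between-person SD and CVs. That unpaired summaries can hide paired disagreement does not.

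Two further inferences should be resisted. The 70-90% band might be read as implying a 12.5% device tolerance (80 × 1.125 = 90), but the documents use it to prescribe intervals and state no accuracy limit. It might also be supposed that 10 adults suffice to confirm such a limit. On the VO₂ scale, a 12.5% load error at 75 W is 93.75/1250 = 7.5%, and about 7% averaged over the span. In simulation an accurate bike would meet that margin in only about 64% of trials at CV 5% and 10% at CV 8%.

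**What to change.** Add a short Stage 1A paragraph to Statistical Methods that:

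- exempts Stage 1A from the median-with-range rule;
- computes each adult's MedBike-minus-reference VO₂ difference (or ratio) at the same setting;
- reports the mean bias with its 95% CI, and the 95% limits of agreement with their CIs;
- plots the difference against workload over 25-125 W and regresses it on workload;
- judges the result against an acceptable limit that the investigators fix and justify in advance;
- states that agreement will not be inferred from similar medians or from p > 0.05;
- says how the two retrospective samples enter, if at all.

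The cost is one paragraph and a small analysis of data already planned, with no extra participants or tests. The downside is that the intervals from 10 adults will be wide, and the report must show them.

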Aside from physical limitations to their exercise capacity, Fontan patient self-confidence toward physical activity is low, as is exercise participation. Studies indicate that amongst youth with CHD, low self-confidence may be a more important predictor of participation than the severity of the disease. Parental overprotection is a common finding in children with CHD with a lasting impact on patient self-confidence and anxieties toward physical activity well into adulthood. Alteration of patient and parental perception and anxieties toward participation in physical activity may improve compliance to exercise training and encourage more positive patient perceptions toward healthy lifestyle habits, including frequent physical activity participation.

Recent technological advances in remote health assessment capabilities and telehealth systems have allowed the development of medically supervised home graduated physical training for adult cardiac patient rehabilitation. The application of such technologies to pediatric congenital heart patients has not been tested. In collaboration with [name] at the Advanced Man Machine Interface Laboratory at the University of Alberta, a custom pediatric remote bike ergometer (MedBike) was developed. This technology provides the medical supervisor with a live-feed of patient video/audio, electrocardiograph (ECG), blood pressure (BP) and blood oximetry signals while enabling remote determination of patient work load through the bike ergometer. The long-term goal is to use this technology to improve patient exercise capacity and to positively influence patient and parental perceptions of the patient's physical ability.

Study Design: Prospective Cohort Study

Study Procedures:

[name] is a member of potential participants clinical care team. He has been added to the study team. Whenever he is available, he will perform early contact by telephone just as the clinic nurse would as described in this section. However, since he is a member of both the study team and the clinical care team there is no need for an early contact letter or permission to contact letter. This process is in adherence with section 55 (section 34) of the Health Information Act. This role will be documented on the delegation log.

CONFIDENTIAL

This material is the property of individual. No part of it may be transmitted, reproduced, published, or used by other persons without written authorization.

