Stage 1B will provide insights as to the feasibility and logistics regarding HIIT programs in the pediatric Fontan patients. This will provide critical information for the investigators as they transition to Stage 2.

Stage 2 (HIIT exercise program): We will evaluate the safety and efficacy of an 8-week, 3 times per week supervised HIIT exercise program in patients with SV physiology.

We aim to recruit 15 subjects with Fontan physiology for Stage 2. Fontan subjects who participated in Stage 1B will invited to continue to Stage 2. If they choose to continue with the HIIT exercise program, Visit 2 of Stage 1B will serve as their first session. Two MedBike exercise ergometers (one pediatric size and one adult size bike) will be housed in the University of Alberta Hospital Rehabilitation Unit with tele-health links to a remote workstation in a separate room. The patients will exercise in a room adjacent to the supervisor workstation with no direct visual or audio contact except for the video/audio feed. This is to help simulate the real-world applicability of having the MedBike at a remote location (such as the subject's home). The HIIT program described above will be applied. The exercise physiologist will again have the ability to modify the program based on the perceived difficulty or ease of it, noting changes that were made. Again, a medical personnel with training in Pediatric Advanced Life Support certification will be present supervising the sessions.

All eligible patients will undergo full cardio pulmonary exercise testing (CPET) and anthropometry assessment of lean muscle mass prior to exercise training and at the end of the training period. For subjects who participated in Stage 1 of the study, their Stage 1 CPET will serve as their initial study. We will document any adverse effects from the 240 training sessions during the study.

Exercise sessions will be based on standardized guidelines for aerobic exercise (ACSM's guidelines for exercise testing and prescription 2013). Heart rate, blood pressure, oxygen saturation and rating of perceived exertion will be monitored during each session.

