We anticipate improved patient CPET performance and a potential increase in measured total lean muscle mass after completing the exercise regimen. We do not anticipate any significant adverse effect from participation in the training sessions thus confirming its safety profile. As we have already performed prototype testing of the custom remote ergometer bike during design and assembly, we do not anticipate any major equipment performance issue or failure. The qualitative research findings will help explain our quantitative findings as we will elicit detailed descriptions of experiences, attitudes, and emotions related to physical activity in children and adolescents with life-limiting/complex CHD. We expect improved health-related quality of life scores in both patient and parental report post exercise training. The impact of a successful exercise training program in pediatrics has immediate benefits in promoting physical activities in children with SV which is currently reduced and likely to continue to decline with increasing age. Exercise training promotes self-confidence and perceived improvement in quality of life. It has the potential to promote a lifetime habit of regular physical activities that is likely to positively impact on a child's long-term cardiovascular and mental health.

Future direction and Knowledge Translation:

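### Total lean muscle mass in growing 10-18-year-olds falls under an uncontrolled pre/post test against zero change, so a significant rise could not be credited to the training

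*Combined protocol and SAP*

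**What the plan says.** All references are to the combined protocol and SAP.

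- **Design.** The opening design line reads "Study Design: Prospective Cohort Study". The Stage 2 description has no untrained group and no control period before training.
- **Population.** Inclusion Criteria: "Stage 2 - SV patients with Fontan circulation age 10 - 18".
- **Programme.** Stage 2 evaluates an "8-week, 3 times per week supervised HIIT exercise program in patients with SV physiology".
- **Measurement.** The Stage 2 text calls for "anthropometry assessment of lean muscle mass prior to exercise training and at the end of the training period". It mentions no z-score, height index, pubertal stage or growth reference.
- **Test.** Statistical Methods gives one inferential rule: "Comparison between pre and post exercise training data will be tested using paired Wilcoxon signed rank sum". The threshold is p < 0.05 and sidedness is not stated. The rule is not limited to max VO2, and it does not name lean mass.
- **Anticipated result.** Anticipated Outcomes and Impact lists "a potential increase in measured total lean muscle mass after completing the exercise regimen" beside improved exercise-test performance.
- **Outcome status.** The primary outcome is the change in max VO2. The secondary outcomes are perceptions and adverse events. Lean mass is in neither list.

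**The concern.** A paired signed-rank test asks whether the changes are centred on zero. That represents no training effect only if an untrained child would show no change over the same weeks. For total lean mass at ages 10 to 18 this cannot be taken for granted, because growth alone can raise it. With one group and no growth reference, the plan cannot divide an observed rise between growth and training.

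What is at stake is one sentence in the report. A significant rise in lean mass could be published as a benefit of HIIT, and used to support the rehabilitation programme that the protocol hopes to establish, although growth alone could have produced it.

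**Working it through.** **1. The plan's own figure.** The only stated sample size is 9, for max VO2. A two-sided paired t-test with standardised effect 1.08, alpha 0.05 and power 0.80 gives n = 9 (power 0.809), so the figure reproduces. It says nothing about lean mass, for which the plan states no size or hypothesis.

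**2. Inputs from the documents.** Interval 8 weeks; threshold 0.05 (two-sided assumed); 15 recruited with up to 30% not completing, so 15 × 0.70 = 10.5, or about 10 completers.

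**3. Inputs assumed.** The documents give no lean-mass growth rate and no SD of the 8-week change. The ranges used are growth of 1 to 6 kg/year and an SD of 0.5 to 1.5 kg.

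**4. Growth over the programme.** Mean change = growth rate × 8/52:

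- 1 kg/year: 0.15 kg
- 2 kg/year: 0.31 kg
- 3 kg/year: 0.46 kg
- 4 kg/year: 0.62 kg
- 6 kg/year: 0.92 kg

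**5. Chance of p < 0.05 with no training effect.** The standardised drift is d = mean change / SD. Normal changes were simulated with mean d and SD 1, and the exact two-sided signed-rank test was applied (10,000 to 20,000 samples per case).

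Check at d = 0: 0.048 at n = 10 and 0.047 at n = 15. The test holds its level when there is no growth, so any excess below comes from the drift.

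| Growth (kg/year) | SD of change (kg) | n = 10 | n = 15 |
|---|---|---|---|
| 1 | 1.5 | 0.06 | 0.06 |
| 1 | 1.0 | 0.06 | 0.08 |
| 2 | 1.5 | 0.09 | 0.11 |
| 2 | 1.0 | 0.14 | 0.18 |
| 3 | 1.0 | 0.25 | 0.36 |
| 3 | 0.8 | 0.35 | 0.53 |
| 4 | 1.0 | 0.40 | 0.57 |
| 6 | 1.5 | 0.41 | 0.58 |
| 6 | 1.0 | 0.72 | 0.90 |

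Repeat runs differ by about 0.01. At the fast, precise end (6 kg/year, SD 0.5 kg), d = 0.92/0.5 ≈ 1.85 and the rate at n = 10 is 0.999.

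**6. Reading.** At n = 10 the rate runs from about 6% to almost 100%. It depends mainly on the ratio of growth to SD. With slow growth and noisy anthropometry it stays near the nominal level; with fast growth and precise measurement it approaches certainty. More completers raise it.

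**The case against.** The strongest case on the other side has five parts.

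- **The measure is peripheral.** Lean mass is not a listed outcome, and no sample size, hypothesis or success criterion depends on it. This stands and keeps the severity low.
- **The plan's wording is cautious.** The rise is called only potential, and the sentence places it after the regimen without saying that the regimen causes it. The test reaches lean mass only through the general pre/post sentence. This stands as a limit on what can be charged to the plan. But lean mass is pre/post data, and its rise appears in a section on anticipated outcomes, so anyone following the plan would test it and would probably read it as a benefit.
- **The test is not at fault.** If children grow, zero change is false and the test correctly detects a change. This is right: the error would be in attributing the change to training. It is the usual limit of an uncontrolled cohort, but it applies directly to a quantity that growth itself can raise.
- **The inflation may be small.** A reader might infer that the error rate is well above 5%. The documents do not support that. They give no growth rate or SD, some participants near 18 may have little growth left, and the slow, noisy end of the range gives only about 6%. No case in the table can be called a central estimate.
- **The interval is 8 weeks.** A reader might infer a longer gap, and hence more growth, for children coming from Stage 1B. The sentence that reuses a Stage 1 baseline covers the exercise test only, not anthropometry.

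Nor does the point carry over to the primary outcome in the same direct way, since peak VO2 is given in ml/kg/min.

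**Conclusion.** The point holds in a limited form. As written, the plan allows a significance test of raw lean mass against zero change in children who may be growing, with nothing to separate growth from training. A significant rise could therefore not be attributed to HIIT. The probability of such a result with no training effect can exceed 5%. The range of about 6% to almost 100% at n = 10 rests wholly on the assumed growth and SD, and on normally distributed changes and a two-sided test. Severity is low: the matter affects how one unlisted measure is interpreted, not the primary result or the sample size.

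**What to change.** **Statistical Methods.** Exempt total lean muscle mass from the significance test. Report its change descriptively (median and range), give each child's interval between measurements in days, and state that the change includes growth.

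**Anticipated Outcomes and Impact.** Do not present a rise in total lean mass as an effect of the regimen.

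**Optional.** If a reference suited to the anthropometric method exists, test the change in the age- and sex-standardised z-score instead. The documents name neither a method nor a reference, and the approach assumes that untrained Fontan patients would track the reference. Lean mass divided by height squared should not be tested against zero as a substitute: it removes only part of the growth and so keeps part of the same problem.

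**Cost.** A sentence or two in each of the two sections, and two measurement dates per child. No new patients or visits are needed, and the primary outcome and sample size do not change. The downside is that raw lean mass has no p-value and the statement about it is less favourable.

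### Seeing no adverse events in 10 to 15 children would not confirm safety: per-child risks up to 18–26% (one-sided 95%) or 22–31% (two-sided 95%) would not be excluded, and the only reporting rule does not fit event counts

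*Combined protocol and SAP*

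**What the plan says.** Safety is part of the purpose of Stage 2. Study Procedures, Stage 2, states: "We will evaluate the safety and efficacy of an 8-week, 3 times per week supervised HIIT exercise program". Adverse events are secondary outcome b, labelled there as the safety profile of the programme. The same Stage 2 section gives the planned exposure: "We will document any adverse effects from the 240 training sessions during the study". It also lists, as examples, the events that stop a session: marked desaturation, chest pain with ischaemic ECG changes, a fall in blood pressure, tachyarrhythmia and bike injury.

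The Statistical Plan sizes the study on max VO2 alone, with a calculated sample size of 9. It then says: "We will recruit 15 Fontan patients in anticipation of up to 30% failure to complete study exercise regimen". On reporting, Statistical Methods says "All data will be reported as median with ranges" and adds a paired Wilcoxon test for pre/post comparisons. It gives no adverse-event proportion, interval, denominator or acceptable limit.

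The one statement on how the safety data will be read is under Anticipated Outcomes and Impact: "We do not anticipate any significant adverse effect from participation in the training sessions thus confirming its safety profile".

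**The concern.** The sentence moves from an expected absence of events to confirmation of safety. With so few children, an event-free result is compatible with a per-child risk that few would accept for a programme described as confirmed safe.

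The reporting rule does nothing to correct this. Whether a child had an event is a yes/no outcome, and a median with a range does not describe it. If no child has an event, the median and range of the counts are all zero, and a reader gets no indication of how large a risk remains compatible with the data.

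What is at stake is the safety statement in the eventual report. Future direction and Knowledge Translation says the study's results will support the case for a paediatric cardiac exercise rehabilitation programme, so an overstated conclusion could carry forward.

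**Working it through.** **The plan's own figure.** The only sample-size figure is n = 9 for max VO2. A paired t-test with effect size 1.08, two-sided alpha 0.05 and power 0.80 gives n = 9 (power 0.809), so it reproduces. Allowing for 30% non-completion, 9 / 0.7 = 12.9, or 13, which 15 covers. None of this concerns safety, and the plan states no safety precision to reproduce.

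**Inputs.**
- Children starting Stage 2: 15 (Sample Size, Stage 2).
- Sessions per child: 8 weeks × 3 per week = 24 (Study Procedures, Stage 2).
- Sessions over which adverse effects are documented: 240 (same section). 240 / 24 = 10 full courses, whereas 15 full courses would be 360 sessions.
- Children expected to complete: 15 × 0.7 = 10.5, about 10 (Sample Size, Stage 2).
- Events: 0, the outcome the protocol anticipates.
- Confidence level: the documents set none for safety. I assume 95% and show it one-sided and two-sided.

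**Upper limit on per-child risk with zero events.** The exact binomial limit is the risk p at which (1 − p)^n equals 0.05 (one-sided) or 0.025 (two-sided, Clopper-Pearson).

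| Children | One-sided 95% | Two-sided 95% |
|---|---|---|
| 15 | 1 − 0.05^(1/15) = 18.1% | 1 − 0.025^(1/15) = 21.8% |
| 10 | 1 − 0.05^(1/10) = 25.9% | 1 − 0.025^(1/10) = 30.8% |

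Risks up to these values are not excluded; risks above them are, at the stated confidence level.

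**The same point from the other side.** If the true per-child risk were 10%, the chance of seeing no event would be 0.9^15 = 21% with 15 children and 0.9^10 = 35% with 10. To exclude 10% with zero events (one-sided 95%) takes ln 0.05 / ln 0.90 = 28.4, so 29 children. To exclude 5% takes ln 0.05 / ln 0.95 = 58.4, so 59.

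**Counting sessions instead.** If sessions were independent, zero events in 240 would give a one-sided limit of 1 − 0.05^(1/240) = 1.24% per session. Over a 24-session course that is 1 − (1 − 0.0124)^24 = 25.9% per child, the 10-child limit on another scale. Likewise 360 sessions give 0.83% per session and 18.1% per child. Sessions are also clustered within 10 to 15 children. If risk is concentrated in particular children, the independence-based per-session limit is too low.

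**The case against.** The strongest reply is that the sentence is narrative. It sits among other hopes, such as better quality-of-life scores, and sets no test, threshold or rule for declaring the programme safe. That stands. A reader might infer that the plan formally accepts safety on zero events, but the Statistical Plan contains no such rule. The sentence still matters, because it is the only statement of how the safety data will be interpreted and the methods offer nothing in its place.

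Three other stronger readings are tempting but not supported:
- That 18 to 26% or more cannot be excluded. At one-sided 95% those values are the top of what is not excluded. Going higher requires the two-sided limits of 22 to 31%.
- That the plan treats 240 sessions as 240 independent observations. It says only that adverse effects across them will be documented.
- That safety is to be the argument for the rehabilitation programme. Future direction and Knowledge Translation refers to the findings and results in general and does not single out safety.

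The denominator can also be disputed. Children who stop early still contribute exposure and events, so a count of all starters is the natural safety set, giving 18% or 22%. The 26% and 31% figures apply if only about 10 contribute, which is what the 240 sessions and the non-completion allowance imply.

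Could Stage 1B help? Adding 10 separate children would give 1 − 0.05^(1/25) = 11.3% one-sided, but each has a single interval session in Stage 1B, which says little about an eight-week course. Those who continue are already among the Stage 2 children.

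Finally, no pilot of this size can establish safety. That is agreed, and it is why the claim should be worded more modestly.

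**Conclusion.** The point holds as one of interpretation and reporting. An event-free Stage 2 would leave per-child risks up to 18% (one-sided 95%) or 22% (two-sided 95%) not excluded if all 15 starters count, and up to 26% or 31% if about 10 contribute. That is preliminary information and not confirmation. Separately, and whether or not events occur, a named secondary outcome has no suitable summary.

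The limits assume zero events of whatever kind is counted, independence between children, and a 95% level that the documents do not set for safety. The 15-child limits describe risk over the training each child actually received, which for non-completers is less than the full course. Nothing here suggests that the programme is unsafe or that recruitment must grow.

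**What to change.** In the Statistical Plan:
- Define the safety denominator as every child who starts Stage 2 training, whether or not the course is completed.
- Report the number and proportion of children with at least one adverse event, with an exact (Clopper-Pearson) two-sided 95% interval. This covers both zero and non-zero counts.
- Use the events listed in Study Procedures, Stage 2, as the events counted. Because that list is introduced by way of example, and the anticipated-outcomes sentence refers only to significant effects, state explicitly which events enter the count.
- Give the number of events and the number of sessions delivered descriptively, without an interval that assumes independent sessions.
- Limit the medians-with-ranges rule to continuous measures.

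Under Anticipated Outcomes and Impact, replace the closing clause about confirmation with a statement that the study will provide preliminary safety data, to be reported with the upper 95% limit on per-child risk.

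The change costs some wording and one interval. Recruitment, visits, data collection and the exercise regimen stay as they are. The downside is a more modest safety claim.
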